12. APENDIXES

Table 1. Prescription Drugs

| Following Implant Surgery |
|---------------------------|
| Rx Amoxicillin 500mg |
| Disp 30 tabs |

| |
|--|
| Sig Take 1 tab three times daily |
| If Penicillin Allergy: Rx Azithromycin 250mg Disp 6 tabs Sig Take 2 tabs 1 st day then 1 tab qd for 4 days |
| Rx Ibuprofen 600mg Disp 20 tabs Sig Take 1 tab every 6h for two days then prn pain |
| Rx Hydrocodone/APAP 5/325mg Disp 20 tabs Sig Take 1 tab every 4-6h prn pain |
| Rx 0.12% Chlorhexidine Rinse Disp 1 X 1.8 oz bottle Sig Rinse with ½ oz for 30 seconds twice daily |

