Subjects in both groups will be instructed to rinse twice daily with 0.12% chlorhexidine gluconate for 30 seconds and avoid brushing or touching the area of extraction for 2 weeks. After 2 weeks, subjects may resume gentle brushing of the surgical site with a soft toothbrush. Sutures will be removed 2 weeks following the surgical appointment. Subjects will return at 1 week and 4 weeks to assess plaque control and wound healing.

Subjects will be given prescriptions for postoperative medications as stated in Table 1. Patient will assume all costs for prescription medications. Temporary appliance to replace the missing tooth will not be delivered as part of the study. However, subjects can have their referring dentists fabricating and delivering a temporary appliance to replace the missing tooth during the first 6 months of the study. The temporary appliance will not be covered by the study.

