5.5 VISIT 4 (DAY 14 +/- 2 DAYS)

Visit 4 may occur within 7 days of visit 3 (+/-2 days). The following procedures will be performed:

- Study personnel will record changes in medical history and concomitant medications since the previous visit and ask continuance criteria questions.
- Participant vital signs (blood pressure and pulse) will be recorded.
- Two (2) GCF samples will be collected from the surgical site for archiving and later regenerative and inflammatory biomarker analysis. The GCF will be collected from the interproximal site of the surgical site without disturbing the healing.
- 3Shape Trios scanning will be completed for later volumetric analysis.
- Sutures will be removed if still present.
- The participant will be instructed to resume oral hygiene measures in the surgical site.
- Adverse events will be monitored and recorded as necessary

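### Table 1 prescribes 1.8 oz of chlorhexidine rinse, a 1.8-day supply on its own directions, where section 5.3 most naturally calls for two weeks (minor, patient care only)

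*Combined protocol and SAP*

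**What the plan says.** Table 1 in section 12 lists the postoperative prescriptions. For the 0.12% chlorhexidine rinse it gives "Disp 1 X 1.8 oz bottle Sig Rinse with ½ oz for 30 seconds twice daily". The row states no number of days, and its heading names implant surgery only.

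The table is nevertheless used after both surgeries:

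- **Extraction.** Section 5.3 (Visit 2, Day 0) says "Subjects will be given prescriptions for postoperative medications as stated in Table 1". It tells both groups to "rinse twice daily with 0.12% chlorhexidine gluconate for 30 seconds and avoid brushing or touching the area of extraction for 2 weeks". At Visit 4 (section 5.5, day 14 +/- 2), "The participant will be instructed to resume oral hygiene measures in the surgical site".
- **Implant placement.** Section 5.9 (Visit 8) points to Table 1 again and gives no rinse duration. Section 5.10 (Visit 9) is where patients are told to resume hygiene at the site. Its timing is printed as two weeks (+/- 2 days) after Visit 9 itself, which can only sensibly mean after Visit 8.

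**The concern.** The quantity and the directions stand in the same table row and do not fit the care that the protocol describes. A patient who fills the prescription as printed and follows the directions has no rinse left before the end of day 2. Brushing of the grafted site is withheld until about day 14, and section 5.4 repeats at the day-7 visit that hygiene there is to be deferred. For most of that period the site would have neither rinse nor brushing. The same gap would follow implant placement.

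What is at stake is routine postoperative care for every participant, in both arms. It is not a matter of inference.

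**Working it through.** The documents state no days-of-supply figure, so there is none to reproduce. The check compares the printed quantity with the printed directions.

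**Inputs**

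- Quantity: 1 bottle of 1.8 oz (Table 1).
- Dose: ½ oz, twice daily (Table 1).
- Period after extraction: 2 weeks (section 5.3, Visit 2, read as covering both the rinse and the brushing ban). Hygiene resumes at day 14 +/- 2 (section 5.5).
- Period after implant placement: about 2 weeks +/- 2 days (section 5.10, read as counted from Visit 8). That rinsing lasts until hygiene resumes is an assumption here, because section 5.9 gives no duration.

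**Supply**

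- Daily use = 0.5 oz x 2 = 1.0 oz.
- Days of supply = 1.8 / 1.0 = 1.8 days.
- Rinses = 1.8 / 0.5 = 3.6, that is 3 full rinses (1.5 oz) with 0.3 oz left.

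**Need, for each surgery**

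| Rinse course | Need at 1 oz/day | Shortfall against 1.8 oz |
|---|---|---|
| 7 days (assumption) | 7 oz | 5.2 oz |
| 10 days (assumption) | 10 oz | 8.2 oz |
| 14 days (natural reading of section 5.3) | 14 oz | 12.2 oz |
| 16 days (late end of the visit window) | 16 oz | 14.2 oz |

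At 14 days the bottle covers 1.8 / 14 = 12.9% of the need, and 14 / 1.8 = 7.8 such bottles would be required. Any course longer than 1.8 days is short, so the mismatch does not depend on the two-week reading. Only the size of the shortfall does.

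**If the figure is a slip of the decimal point.** A bottle of 18 oz would last 18 / 1.0 = 18 days, which exceeds 16, and there would be no shortfall. This illustrates how the figure could have arisen. The documents do not give the intended size.

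**The case against.** **The number may be a reading error.** The case rests on one decimal point, in a table that is visibly broken in the extracted text. If the original shows a larger size, the quantity is not an error in the plan. This stands as a reason to check the source first. It does not dispose of the point: the digits read cleanly, and nothing else in the row looks corrupted.

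**The practical harm is limited.** Patients receive prescriptions and pay for them, so the study is not described as handing out this bottle, and a refill or a different size could be supplied. The same table prescribes an antibiotic. Section 5.3 also adds "Subjects will return at 1 week and 4 weeks to assess plaque control and wound healing", so a shortage could be noticed at the week-1 visit. All of this holds and keeps the point minor. None of it makes the quantity right.

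**The duration is already given.** Section 5.3 most naturally applies its two weeks to the rinse as well as to brushing, so for the extraction visit a missing duration in Table 1 is a matter of wording only. That is accepted.

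**Tempting inferences that the documents do not support**

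- A reader might argue that every other row fits its directions, so that the rinse row must be a misprint. Only the azithromycin row can test this: "Disp 6 tabs Sig Take 2 tabs 1 st day then 1 tab qd for 4 days" gives 2 + 4 = 6 tablets, which matches. The amoxicillin directions, "Sig Take 1 tab three times daily", state no number of days, so 30 / 3 = 10 days agrees with nothing printed. A misprint is likely mainly because three full rinses make little sense beside a two-week ban on brushing.
- A reader might infer that poor plaque control could bias the comparison. The rinse instruction and the prescription are the same in both arms, so the plan creates no imbalance here.

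**Conclusion.** Minor, and wrong as written. Table 1 supplies 1.8 days of rinse against a need of 14 oz for two weeks, or 16 oz at the late end of the visit window, a shortfall of 12.2 to 14.2 oz for each surgery. The 1.8-day figure needs no assumption beyond the printed number being correct. The size of the shortfall rests on reading section 5.3 as a two-week rinse and, after implant placement, on rinsing until hygiene resumes at Visit 9.

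The documents do not show that a two-day course was intended, nor that any patient would in fact go without rinse. A misprint is the likeliest explanation, and a reading error in the text remains possible. No endpoint, power figure or analysis is touched.

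**What to change.** 1. Check the bottle size against the original document and confirm the intended size with the investigators.
2. If it does read 1.8 oz, change the entry "Disp 1 X 1.8 oz bottle" to at least 14 oz for each surgery, or 16 oz to cover the 2-day visit window.
3. Make the Table 1 heading cover both extraction and implant surgery, since sections 5.3 and 5.9 both rely on it. This applies whatever the original bottle size proves to be.
4. As a wording clarification only, add a two-week duration to the rinse directions, in line with section 5.3.

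The cost is one quantity, one heading and a few words in a single table. Design, sample size and analysis do not change.
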